3.4.3 Exclusion Criteria

Subjects will be excluded if they fall under any of the exclusion criteria described in Table 3.4.3-1.

Tab	le 3.4.3-1 Exclusion Criteria
1	 Patients who have dementia or memory impairment other than dementia of the Alzheimer's type, such as the following: Frontotemporal dementia
	Lewy body dementia
	• Vascular dementia
	Dementia secondary to head trauma
	Substance-induced persistent dementia
	Dementia due to human immunodeficiency virus infection
	Dementia due to prion disease
	• Dementia due to Parkinson's disease (including Parkinsonian diseases such as progressive supranuclear palsy and basal ganglion degeneration)
	Dementia due to Huntington's disease
	• Dementia due to other general medical conditions (eg, subdural hematoma, normal pressure hydrocephalus, brain tumor, endocrine disorders, nutritional disorders, or infections)
	Dementia due to multiple diseases
	Dementia not otherwise specified
2	Patients diagnosed with delirium between 30 days before the screening examination and baseline evaluation according to DSM-5.
3	Patients diagnosed with any of the following disorders according to DSM-5:Schizophrenia spectrum and other psychotic disorders
	Bipolar and related disorders
	Major depressive disorder
	However, patients who have major depressive disorder but whose condition is stable and asymptomatic within 30 days before the screening examination may be included. In regard to patients whose condition has been stabilized by medication, it should be noted that the use of antidepressants is prohibited from 7 days before baseline evaluation up to the completion of the examinations scheduled at the completion or discontinuation of IMP administration (see Section 4.1 Prohibited Medications).
4	Patients with psychological symptoms or behavioral problems clearly due to other diseases or a drug
5	substance.
5	 Patients with a complication of nulmonary embediam
	• Fatients with a complication of pullionary emborism. However, natients with asymptomatic cerebral infarction or uncertain transient ischemic attack may
	be included.
	In regard to history of stroke or transient ischemic attack, a patient may be included if a medical monitor checks the patient's symptoms and judges that they will have no influence on the efficacy and safety of the IMP.

17	Patients meeting any of the following criteria at screening:Hypotension with symptoms
	• Orthostatic hypotension in which blood pressure after at least 3 minutes of standing is ≥ 30 mmHg lower for systolic blood pressure (SBP) or ≥20 mmHg lower for DBP compared with pressures in the supine position before standing
18	Patients with the following abnormal laboratory test values at screening (assessed on the basis of the results from the central laboratory):
	• Platelet count: $\leq 75,000/\text{mm}^3$
	• Hemoglobin: $\leq 9 \text{ g/dL}$
	• Neutrophil count: $\leq 1000/\text{mm}^3$
	• Aspartate aminotransferase (AST) and alanine aminotransferase (ALT): > 2 times the upper limit of normal (ULN)
	• Creatine phosphokinase (CPK): > 3 times ULN (however, this does not apply if the medical monitor judges that there will be no medically significant problems)
	• Albumin: $< 3 \text{ g/dL}$
19	Patients whose body weight at screening or baseline evaluation is < 30 kg

Protocol 331-102-00088

Tab	le 3.4.3-1 Exclusion Criteria
20	Patients whose Sheehan Suicidality Tracking Scale (S-STS) score at screening or baseline evaluation matches any of the following criteria or who are judged by the investigator or subinvestigator to be at high risk of suicide:
	• Patients with a score of 3 or 4 on any of S-STS Questions 2, 3, 4, 5, 6, or 11
	• Patients with a score of 2 or more on any of S-STS Questions 1a, 7, 8, 9, 10, or 12
21	 The following patients falling under the contraindications in the package insert for REXULTI[®]: Patients in a coma
	• Patients under the strong influence of central nervous system depressants, including barbiturate analogs/anesthetics
	Patients receiving adrenaline
	• Patients with a history of hypersensitivity to the components of REXULTI [®]
22	Patients with thyroid disease (not including patients whose condition has been kept stable via drug therapy for at least 3 months prior to the acquisition of informed consent) or patients who show
	abnormal values for thyroid-stimulating hormone (TSH) and free thyroxine (FT4) in the screening examination
23	Patients who are likely to require any prohibited medications during the trial period
24	Patients who have previously taken brexpiprazole
25	Patients who have previously received antipsychotic medication for agitation associated with dementia of the Alzheimer's type and whose condition has been judged to be treatment resistant. Cases in which treatment has to be stopped owing to adverse events are not counted as treatment resistant.
26	Patients who have undergone disease-modifying treatment for dementia of Alzheimer's type (eg, amyloid β vaccine) within 6 months before the start of IMP administration
27	Patients who have taken any investigational drug within 30 days prior to informed consent
28	Patients who are bedridden and require assistance for excretion, eating, and changing clothes
29	Women who are nursing before the administration of IMP or have a positive pregnancy test result at screening
30	Sexually active men or sexually active women of childbearing potential who will not agree to practice 2 different methods of birth control or to remain abstinent during the trial and for 30 days after the final IMP administration. For birth control, two of the following methods must be used: vasectomy, tubal ligation, vaginal diaphragm, intrauterine contraceptive device (IUD), oral contraceptives, or condom with spermicide.
31	Patients who otherwise were judged by the investigator or subinvestigator to be unsuitable for participation in the trial

Men without the ability to procreate are defined as those who have had bilateral orchidectomy, and women who are incapable of pregnancy are defined as those who have had bilateral oophorectomy or hysterectomy or who have been postmenopausal for at least 12 months.

Subjects must agree to the restrictions described in Section 4 Restrictions.

[Rationale for the exclusion criteria]

1 to 4 These criteria are specified to exclude patients who would be inappropriate for this trial. 5 to 21 These criteria are specified in view of safety.

22 to 27, 31 These criteria are specified for the appropriate assessment of safety and efficacy.

28 This criterion is specified for the appropriate assessment of efficacy and in view of safety.²⁰ 29, 30 These criteria are specified in consideration of safety, as the safety of brexpiprazole during pregnancy or while breastfeeding has not yet been established.

3.5 Requirements for Caregivers

A caregiver who meets the following criteria will be designated as the main caregiver in the trial:

- Is able to obtain the patient information required for evaluation (24-hour information wherever possible on the patient's activities including toilet use, eating, bathing, changing, and other daily activities) during the trial period and provide this information during the inquiries on trial evaluation items; and
- Provides the patient with care and can observe the patient's condition in at least 4 days per week for 4 hours or more a day, starting from 14 days before the day of baseline evaluations to the completion of the examinations scheduled at the completion or discontinuation of IMP administration.

If there are multiple caregivers in charge of the patient's care, the main caregiver will not only provide patient information from his or her own observations but also obtain from the other caregivers information on the patient's condition during those periods when the patient was not under his or her observation and provide all patient information required for evaluations during the inquiries on the trial evaluation items.

To the extent possible, the same main caregiver will respond to queries on the trial evaluation items from 14 days before the day of baseline evaluations to the completion of examinations scheduled at the completion or discontinuation of IMP administration. If the main caregiver is unable to respond to queries, a substitute caregiver is allowed to respond to queries on the trial evaluation items. However, to the extent possible, queries on the trial evaluation items at the time of baseline evaluation and at the completion or discontinuation of IMP administration should be answered by the person who was designated as the main caregiver at the start of the trial. A substitute caregiver should be able to obtain patient information required for evaluations from other caregiver and provide the same information as would have been provided by the main caregiver during inquiries on the trial evaluation items, and should be selected from among the caregivers in charge of the patient's care. Queries at the conclusion of IMP administration will also be answered by a caregiver who is in charge of the patient's care and is able to provide patient information required for evaluations.

3.6 Endpoints

3.6.1 Primary Endpoint

The primary endpoint is change in CMAI total score from baseline to Week 10.

The CMAI is a scale to assess the frequency of specific agitation symptoms. The Practice Guideline for Dementia 2017 recommends the NPI, Behavioral Pathology in Alzheimer's Disease, and CMAI for assessment of BPSD. The CMAI evaluates the frequency of occurrence of specific agitation for the preceding 2 weeks and is used globally for assessment of agitation.^{22,28} Therefore, the CMAI is the most appropriate scale for evaluating the efficacy of brexpiprazole for agitation associated with dementia of the Alzheimer's type, which is the primary objective of the trial. Furthermore, the CMAI was adopted as the primary endpoint in the 2 overseas trials (Trial 331-12-283 and Trial 331-12-284).

3.6.2 Secondary Endpoints

- Changes in CMAI subscales (Aggressive Behavior, Physically Non-aggressive Behavior, and CMAI Verbally Agitated Behavior) from baseline to Week 10
- Change in Clinical Global Impression–Severity of Illness (CGI-S) from baseline to Week 10
- Clinical Global Impression–Global Improvement (CGI-I) at Week 10

3.6.3 Exploratory Endpoints

3.6.4 Safety Endpoints

- Adverse events
- Physical examinations

- Laboratory tests
- Vital signs
- Body weight
- Twelve-lead electrocardiogram (ECG)
- Pregnancy test (for women of childbearing potential [WOCBP] only)
- Drug-Induced Extrapyramidal Symptoms Scale (DIEPSS)
- Abnormal Involuntary Movement Scale (AIMS)
- Barnes Akathisia Rating Scale (BARS)
- Sheehan Suicidality Tracking Scale (S-STS)

3.6.5 Pharmacokinetic Endpoint

Plasma concentrations of OPC-34712 at Week 10 of brexpiprazole administration

3.6.6 Pharmacogenomic Endpoint

CYP2D6 genotype

3.6.7 Other Endpoints

- Alzheimer's Disease Cooperative Study–Activities of Daily Living (ADCS-ADL)
- MMSE
- EuroQol 5-dimension 5-level health questionnaire (EQ-5D-5L)

3.7 Measures to Minimize/Avoid Bias

Subjects who meet all the inclusion criteria and do not fall under any of the exclusion criteria will be randomly assigned to the brexpiprazole 1 mg/day group, the brexpiprazole 2 mg/day group, or placebo group at a randomization ratio of 3:4:4. The IMP allocation will be performed using a dynamic allocation method. The details of the randomization method will be described in a separately produced procedural guide for dynamic allocation.

This is a double-blind trial. The IMP allocation manager will prepare a "Table of randomization scheme and codes" (hereinafter randomization table) and conduct IMP coding according to the operating procedures for randomization. The IMP allocation manager will prepare an emergency code list for emergencies, such as when an SAE occurs.

The treatment assignment code will be revealed to neither the subject (including any representatives or caregivers) nor the investigator. The sponsor's staff involved in the

trial (except for those of the Department of Pharmacovigilance [PV department]), including contract research organizations (excluding the bioanalytical laboratory, genetic analysis laboratory, and IDMC), will also remain blind to the treatment assignment codes for the duration of the trial. Prior to the start of the trial, those who are involved in packaging the IMP and the sponsor will confirm that the IMP is not identifiable. The randomization table will be strictly retained until unblinding is performed after finalization of all the case report forms (CRFs) and database.

The emergency code break information will be managed by the IWRS until the completion of the trial. In the event that a subject has a medical emergency and the knowledge of the treatment assignment code is necessary for treatment, the emergency key may be opened for the subject in question (see Section 5.6 Procedure for Breaking the Blind).

The results of CYP2D6 genotyping and plasma drug concentration measurements should not be disclosed until unblinding at the end of the trial. The CYP2D6 genotyping and plasma drug concentration measurements should be performed at the designated laboratories and not at the clinical laboratories of the trial sites.

^gBlood pressure and pulse rate will be measured in the order of supine, sitting, and standing positions.

^hEligibility will be assessed based on consecutive triplicate ECG measurements (central reading). The third measurement can be omitted if neither the first nor second measurement (central reading) meets the exclusion criteria.

- ¹Pregnancy test (HCG test) will be performed for WOCBP only. If urinary test is positive, serum test will be performed.
- ^JBlood sampling will be performed before IMP administration if the IMP is administered in Week 10 but does not need to be performed at the time of discontinuation.
- ^kIf blood sampling is not performed for any other test item or for some reason cannot be performed at the time of baseline evaluation, or if blood resampling is necessary, blood sampling will be performed during the trial period.

^lOptional

^mIf for some reason it is not possible to perform blood sampling at this time or if blood resampling is necessary, blood sampling will be performed during the trial period.

Table 3.8-2Allowable Time Windows for Evaluations, Tests, and Observations						
Test Point		Base Date	Allowable Time Window From the Base Date			
Screening period		At the start of screening	Day -42 to Day -2			
Baseline evaluation date		Day 1	Day -1 or Day 1			
Week 1		Day 8	Day 6 to Day 10			
Week 2		Day 15	Day 13 to Day 17			
Week 4		Day 29	Day 27 to Day 31			
Week 6		Day 43	Day 40 to Day 46			
Week 8		Day 57	Day 54 to Day 60			
Week 10		Day 71	Day 68 to Day 78			
Follow-up period ^a		28 days after the final administration of IMP	23 to 35 days after the final administration of IMP			

^aFollow-up observation will not be performed for subjects who have transitioned to the extension trial and commenced IMP administration.

The date of starting IMP administration is designated as Day 1.

All baseline observations, tests, and evaluations will be performed on the day before the start of IMP administration (Day -1) and the day of starting IMP administration (Day 1). CMAI, CGI-S,

, and must be performed on the same day.

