The Practice Guideline for Dementia 2017 instructs as follows for agitation: "Personcentered-care is the basis. The reason(s) and cause(s) of symptoms should be considered and measures to resolve them should be sought. Another effective approach is for caregivers to learn appropriate skills for conversing with patients with dementia and to exercise these skills. As nonmedication therapies, the efficacy of group activities, music therapy, tactile care, and massage has been demonstrated, and use of these therapies should also be considered" and "if the patient does not respond adequately to nonmedication therapies, medication should be considered."¹⁷ This clearly implies that if

agitation does not respond adequately to nonmedication therapies, medication needs to be considered. While the guideline states that "medication should be introduced only after sufficient efforts have been made to reduce BPSD with nonmedication therapies," it lists "aggression that endangers self or others" as one of the "exceptions to preferentially introduce medication."¹⁸ According to the guideline, immediate consideration of medication cannot be avoided in some patients with aggressive agitation associated with dementia of the Alzheimer's type.

However, in Japan there are no drugs indicated for agitation and all drugs are administered as off-label use. Although it is off-label use, the Practice Guideline for Dementia 2017 states the following regarding medication: "The efficacy of atypical antipsychotics such as risperidone and aripiprazole has been demonstrated. Use of Yokukansan, tiapride, carbamazepine, sertraline, escitalopram and trazodone should also be considered."¹⁷ The results of a meta-analysis of dementia patients in clinical trials of atypical antipsychotics, for which efficacy has been demonstrated according to the guideline, showed a mortality rate 1.54-fold higher in the atypical antipsychotic group compared with the rate in the placebo group,¹⁹ showing a risk of death. These findings show that sufficient evidence is lacking for all medications indicated for agitation and the use of atypical antipsychotics needs to be considered despite the reported safety risk. Due to these circumstances, there are unmet needs for a drug-based approach to the treatment of agitation.

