3.8.8 Independent Data Monitoring Committee

The IDMC will be established to avoid exposing subjects to all potential risks (including the risk of death) during the trial period and to ensure the safe conduct of the trial. The IDMC will meet regularly and as needed to review the subject demographics and AEs and to give advice on the appropriateness of continuing the trial or the necessity of modifying the protocol.

The sponsor will designate the following as IDMC members:

The IDMC members, their roles, and other details will be specified in a separate procedure.

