3.9.3.3 Withdrawal of Consent

All subjects (including their legal representatives and caregivers) have the right to withdraw their consent from further participation in the trial at any time without prejudice. Subjects cannot withdraw consent for use of data already collected as part of the trial, but only for future participation. The investigator or subinvestigator can also discontinue a subject's participation in the trial at any time if medically necessary. Unless the subject provides their written withdrawal of consent or there is other written documentation by the investigator or subinvestigator confirming the subject's verbal intent to completely withdraw from the trial, subjects should be followed for all protocol-specified evaluations and assessments, if possible.

Complete withdrawal of consent requires refusal by a subject of ALL of the following methods of follow up (these methods of follow up will also be noted in the trial ICF):

- Participation in all follow-up procedures specified in the protocol (whether in-clinic, by telephone, or by an in-home visit).
- Participation in a subset of protocol specified follow-up procedures (by a frequency schedule and method, as agreed by subject and staff).
- Contact of the subject by trial personnel, even if only by telephone, to assess current medical condition, and to obtain necessary medical or laboratory reports relevant to the trial's objectives.
- Contact of alternative person(s) who have been designated in source documents as being available to discuss the subject's medical condition, even if only by telephone, mail, or e-mail (eg, family, spouse, partner, legal representative, friend, neighbor, or physician).
- Access to medical information from alternative sources (eg, hospital/clinic medical records, referring doctor's notes, public records, dialysis, transplantation or vital registries, social media sources).

Withdrawal of consent is a critical trial event and therefore should be approached with the same degree of importance and care as is used in initially obtaining informed consent. The reasons of a subject for an intended withdrawal need to be completely understood, documented, and managed to protect the rights of the subject and the integrity of the trial. A subject may initially express their desire to discontinue IMP administration, which is

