5.2 Eliciting and Reporting Adverse Events

The investigator or subinvestigator will periodically assess subjects for the occurrence of AEs. To avoid bias in eliciting AEs, subjects should be asked the non-leading question: "How have you felt since your last visit?" All AEs (serious and nonserious) reported by the subject must be recorded in the source documents and CRFs provided by the sponsor. The event name, date and time of onset, date and time of recovery, seriousness, severity, causal relationship to IMP, actions taken regarding IMP administration, and outcome thereof will be recorded in the CRF. The period for AE and SAE collection is defined as the period from after a subject has signed the ICF to the date of trial completion.

Use medical terminology in AE reporting. Adverse events should be reported as a single unifying diagnosis whenever possible or, in the absence of a unifying diagnosis, as individual signs or symptoms. Exacerbation or disease progression should be reported as an AE only if there are unusual or severe clinical features that were not present, or experienced earlier, or not expected on the basis of the course of the condition.

Worsening of severity and seriousness of reported AEs must be reported as new AEs in the CRF.

In addition, the sponsor must be notified immediately by e-mail of any IREs according to the procedure outlined below, in Section 5.3 Immediately Reportable Events. Special attention should be paid to recording hospitalization and concomitant medications.

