5.7.2 Follow-up of Serious Adverse Events and Immediately Reportable Events

This trial requires that subjects be actively monitored for SAEs and IREs up to the end of trial date (final day of observation).

Serious AEs and IREs that are identified or ongoing at the end of trial date must be recorded in the AE section of the CRF. Between the end of trial date for the individual subject and the end of trial date for the last subject, if any new information regarding an SAE or IRE becomes available (eg, the event is resolved), this must be reported to the sponsor using the IRE form and so on, and the information must be recorded in the AE section of the CRF. The investigator or subinvestigator will follow SAEs and IREs, and will continue to report any significant information to the sponsor until the events are

resolved or stabilized, or the subject is lost to follow-up or has died, using the IRE form and so on.

5.7.3 Follow-up and Reporting of Serious Adverse Events and Immediately Reportable Events Occurring After the End of Trial Date (Final Day of Observation)

Any new SAEs or IREs reported to the investigator or subinvestigator, which occur after the end of trial date (final day of observation) and are determined by the investigator or subinvestigator to be associated with the use of the IMP, should be reported to the sponsor. This includes SAEs and IREs that are captured on follow-up telephone contact or at any other time point after the defined trial period. The investigator or subinvestigator will follow SAEs and IREs identified after the defined trial period and continue to report any significant follow-up information to the sponsor until the events are resolved or stabilized, or the subject is lost to follow-up or has died, using the IRE form and so on.

6 Statistical Analysis

The definitions of the datasets for analysis and the analysis methods for the specified endpoints are described below. The statistical analysis plan details are described in a separate Statistical Analysis Plan. The Statistical Analysis Plan will be finalized prior to data lock.

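### For subjects who stop treatment in about the first five to seven weeks, no scheduled contact or vital-status check reaches Day 71, so deaths through Week 10 are not systematically collected

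*Protocol*

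**What the plan says.** Protocol 1.1 cites a meta-analysis of dementia trials that found "a mortality rate 1.54-fold higher in the atypical antipsychotic group" than on placebo. Protocol 2.1 gives that report as the reason for some exclusion criteria and for setting up the Independent Data Monitoring Committee (IDMC). Protocol 3.8.8 names death among the risks the committee is there to guard against.

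A subject who stops early has a discontinuation examination and one follow-up visit. Table 3.8-2 sets that visit at "28 days after the final administration of IMP", with a window of "23 to 35 days after the final administration of IMP". Protocol 3.1 ends the subject's trial period there. Protocol 5.2 closes event collection at trial completion: "The period for AE and SAE collection is defined as the period from after a subject has signed the ICF to the date of trial" … In Table 3.8-1 the Week 10 and discontinuation assessments share one column, and the only later column is the follow-up visit.

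Three provisions reach beyond that visit:
- Protocol 3.9.3.2: if the drug was stopped for an adverse event, that event is followed until it resolves or stabilises, contact is lost or the subject dies.
- Protocol 5.7.2: serious events already identified or ongoing are recorded and followed in the same way. Neither this provision nor 3.9.3.2 has a causality condition.
- Protocol 5.7.3: new serious events after the final day of observation that the investigator determines "to be associated with the use of the IMP, should be reported to the sponsor".

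SAP 9.2 summarises treatment-emergent events with a fatal outcome. It has no mortality analysis to a fixed day.

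**The concern.** Follow-up is counted from the last dose, not from the start of treatment. How long a subject is watched for death therefore depends on when that subject stopped, and stopping may differ by arm. A new fatal event after the follow-up visit is captured only through one investigator's causality judgement. A comparison of death rates between randomised arms needs no such judgement.

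At stake is how to read the death table for a risk that the protocol itself names. A crude count of fatal events would mix completers followed for about four weeks after the last dose, completers who enter the extension and end at Week 10, and early stoppers last seen well before Week 10.

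**Working it through.** **Does participation end at the follow-up visit?** The synopsis gives up to 20 weeks per subject. Screening of 42 days, treatment of 70 days and follow-up of 28 days make 140 days, and 140 / 7 = 20 weeks. This reproduces, so the plan leaves no time for contact after the follow-up visit. The plan has no figure of its own for mortality follow-up.

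**Inputs.** Follow-up falls 23, 28 or 35 days after the last dose (Table 3.8-2). The Week 10 target is Day 71, with a visit window of "Day 68 to Day 78". The last planned dose is Day 70 (Table 3.2.1-1). The sample size is 407 (Protocol 6.1).

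**Formula.** For a last dose on Day D and a follow-up visit w days later, observation ends on Day D + w. The gap to Week 10 is max(0, 71 − (D + w)).

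| Last dose | Observation ends (w = 23 / 28 / 35) | Gap in days |
|---|---|---|
| Day 1 | 24 / 29 / 36 | 47 / 42 / 35 |
| Day 14 | 37 / 42 / 49 | 34 / 29 / 22 |
| Day 28 | 51 / 56 / 63 | 20 / 15 / 8 |
| Day 35 | 58 / 63 / 70 | 13 / 8 / 1 |
| Day 42 | 65 / 70 / 77 | 6 / 1 / 0 |
| Day 48 | 71 / 76 / 83 | 0 / 0 / 0 |

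The last uncovered last-dose day is therefore 47, 42 or 35. From Day 48 on, every permitted visit date reaches Day 71. By comparison, a completer who does not enter the extension is observed to about Day 70 + 28 = 98.

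**Size, by assumption only.** The documents give no dropout rate or timing. Take 10% to 30% dropout, with last doses spread evenly over Days 1 to 69.
- Share of dropouts uncovered: 42/69 = 61% at the target visit (35/69 = 51% to 47/69 = 68% across the window).
- Subjects affected: 407 × 0.10 × 42/69 = 24.8, and 407 × 0.30 × 42/69 = 74.3. That is about 25 to 74 (21 to 83 across the window).
- Mean gap per dropout at the target visit: (42 × 43 / 2) / 69 = 903/69 = 13.1 days.
- Share of person-days to Day 71: 0.10 × 13.1/71 = 1.8%, and 0.30 × 13.1/71 = 5.5% (1.3% to 6.9% across the window).

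The head-count includes subjects who would still be followed for a known event and subjects who refuse all contact, so it overstates how many have no route by which a death would be learned.

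**Can the other provisions supply a Day 71 status?**
- Protocol 3.9.3.3 says that, short of full withdrawal, "subjects should be followed for all protocol-specified evaluations and assessments, if possible". Nothing is specified after the follow-up visit.
- Protocol 3.12 seeks survival status only for subjects who can no longer be contacted. It does not apply to someone who attended the follow-up visit.
- The clause in 3.9.3.2 applies when the drug was stopped for an adverse event. Becoming bedridden, lack of efficacy, need for a prohibited drug and a change of care environment are listed as separate reasons.

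**Do deaths during follow-up count?** SAP 3.4 drops data from 7 or more days after the final dose, for all endpoints. SAP 9.2 has an onset category after trial treatment. The SAP does not say which governs deaths.

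**The case against.** The strongest reply is that the main harm pathway is already covered. A subject who deteriorates, stops because of that event and dies of it later is followed to death under 3.9.3.2, and 5.7.2 does the same for any known serious event. A later death judged drug-related is reportable under 5.7.3. What remains is a new event, starting after the follow-up visit and judged unrelated. Counting deaths on treatment plus about four weeks is also a coherent exposure-based approach, and SAP 9.1 shows exposure by arm. All of this stands, and it confines the point to new events.

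One could also argue that 5.7.2 keeps every subject under active monitoring until the whole trial ends, because 3.8.7 defines the end-of-trial date by the last subject. But 5.7.2 and 5.7.3 equate that date with the final day of observation, 5.7.2 separately names an end date for the individual subject, and 3.1 ends the subject's trial period at the follow-up visit. The subject-level reading fits better.

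A reader might go further than the documents allow in four ways:
- That mortality through Week 10 is unknown for early dropouts in general. Those with a last dose on Day 48 or later are covered at any permitted visit date, and 3.9.3.3 and 3.12 give partial routes for others.
- That every later death counts only if judged drug-related. This ignores 3.9.3.2 and 5.7.2.
- That the IDMC sees truncated counts. Its procedure and the interim analysis plan are separate documents.
- That the trial was built to watch mortality. Its objectives are superiority on agitation, safety and the optimum dose. Death is a named reason for the IDMC and some exclusions.

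**Conclusion.** The point holds in a limited form. For a last dose on or before Day 42 at the target visit date (Day 35 to Day 47 across the window), vital status at Day 71 is not systematically collected, and a death from a new event after the follow-up visit need be reported only if judged drug-associated. Fatal-event counts therefore cover observation periods that depend on when subjects stopped.

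The date arithmetic rests on the documents alone. The 25 to 74 subjects and roughly 2% to 6% of person-days rest on an assumed 10% to 30% dropout with even timing. The documents give no expected death rate for this trial, so the number of missed deaths cannot be estimated. Nor do they show that the cited 1.54-fold figure came from all-cause deaths counted without causality judgement, or how often investigators here would judge a death unrelated. This is a low-cost improvement to a defensible design, not an error in the plan.

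**What to change.** - **Protocol 3.8.1.6 and Table 3.8-1:** for every treated subject who stops early and has not refused all contact, record vital status at Day 71, with date and cause of any death, regardless of causality. Use the telephone, alternative-contact or records routes already listed in 3.9.3.3.
- **SAP 9.2:** beside the existing table of fatal treatment-emergent events, add deaths from any cause through Day 71 by randomised arm.
- **SAP 3.4:** state that the exclusion of data from 7 or more days after the final dose does not apply to deaths.

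The cost is one check per early stopper, one case report form item and one table. Some deaths captured this way will occur well off drug and dilute the on-treatment picture, but the existing table is unchanged and still shows that picture.
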